Patterns of renal tubular disorders in Egyptian children: a single center study

NCT04845815

Soh-Med-21-04-04

Date: 12th of April 2021

Sohag University
Faculty of Medicine
Department of Pediatrics

Patterns of renal tubular disorders in Egyptian children: a single center study

Thesis

Submitted for Partial Fulfillment of the Master Degree in Pediatrics

Presented by

[name]

M.B.B.Ch.E.

Resident in Pediatric Department

Sohag University Hospital

Under Supervision of

prof. [name]

Professor and head of Pediatric department

Faculty of Medicine, Sohag University

[name] [name]

Lecturer of Pediatrics

Faculty of Medicine, Sohag university

Sohag university

2020 – 2021

Patterns of renal tubular disorders in Egyptian children: a single center study

Introduction

Fluids, electrolytes, and acid-base regulations are the main functions of renal tubules(1). Defects of these functions give rise to several disorders(2). In Egypt, little data is available. Many of these cases are diagnosed late, therefore Early suspicion for diagnosis can improve the overall clinical outcome of these children. Starting management early will help those children have a better life. Therefore, awareness about these disorders and long-term outcome is important(3). We present the clinical characterizations of many tubular disorders and the follow up in our center with emphasis on growth and renal functions outcomes.

Aim of the work

The aim of this study is to reveal the different clinical presentations and the main lab features of renal tubular disorders in children to promote early recognition and management in addition to monitoring growth and glomerular filtration rate.

Patients and methods

-Place of the study:

Sohag University Hospital, Pediatric Department, Nephrology Unit.

-Type of the study: Retrospective and prospective study.

-Study period: 6-12 months after protocol acceptance.

-Patients: -

This study will include all children who have renal tubular disorders (inpatient and outpatient) in the Pediatric Department, Sohag University Hospital.

- Inclusion criteria: -

All children aged from one month to 18 years who have renal tubular disorders.

Exclusion criteria:

Children who have renal tubular disorders secondary to drugs, intoxication, obstructive uropathy or transient in nature.

-Methods:

Records of all children who have renal tubular disorders in the nephrology center from 2015 to 2020 and the children following up from April 2021 to December 2021 will be subjected to:

1-History taking with emphasis on age, age at diagnosis, sex, family history, Failure to thrive, polyuria, polydipsia, consanguinity, dehydration episodes, lack of appetite, vomiting, seizures, weakness, photophobia, and deafness.

2-Complete physical examination with emphasis on general condition, signs of rickets, polyuria (>4 ml/kg/hour), bone deformities and developmental milestones.

3-Growth assessment was done by recording height and weight according to the WHO growth charts and z scores. (Failure to thrive means weight and height below the 3rd centiles).

4-Investigations done for children included:

- a- Blood gases and anion gap estimation
- b- Electrolytes: serum sodium, potassium, calcium, chloride, and phosphorus
- c- Urine analysis and urinary calcium creatinine ratio
- d- Estimation of GFR
- e- Renal ultrasound
- f- Complete blood count
- g- Others may be needed e.g., bone radiograph, serum magnesium, and urinary chloride.

Metabolic acidosis means decreased serum HCO₃ concentration and pH below 7.35.

Metabolic alkalosis means elevated serum HCO₃ concentration and pH above 7.45.

The glomerular function was assessed by estimated glomerular filtration rate (eGFR) calculated using Schwartz formula.[5]

Statistical analysis:

We expressed the data as percentage, median with range. Data was analyzed using Wilcoxon test to compare the diverse groups of renal tubular disorder. Qualitative data was presented as number and percentage and compared using Chi square test. P value < 0.05 was considered significant. Serial weight and height were measured and z scores and percentiles were calculated. GFR was estimated and monitored using Schwartz formula(4).

-Ethical consideration: -

The protocol will be submitted to Medical Research Ethical Committee for approval.

Written informed consent will be taken from all participating patients or their families.

Results:

58 children with renal tubular disorders were candidates. Duration of follow up ranges from (6-132) month with median 12 month. In our study, there were 33 males and 25 females.

Patterns of renal tubular disorders:

Various renal tubular disorders were noticed. DRTA and Barter S were the most common encountered tubulopathies.

Diagnosis:

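### January to March 2021 falls in neither the record window nor the prospective window, although the study says it includes all children

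*Combined protocol and SAP*

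**What the plan says.** Under Patients and methods the design is described as "Retrospective and prospective study". The Patients paragraph claims completeness: "This study will include all children who have renal tubular disorders (inpatient and outpatient) in the Pediatric Department, Sohag University Hospital". The inclusion criterion, "All children aged from one month to 18 years who have renal tubular disorders", sets an age range and no calendar limit.

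The calendar limits appear only at the start of Methods, which names two sources in one phrase, covering records of affected children "in the nephrology center from 2015 to 2020 and the children following up from April 2021 to December 2021". Both go through the same list of history, examination, growth assessment and investigations. Age at diagnosis is listed under history: "History taking with emphasis on age, age at diagnosis, sex, family history". Nothing says where height, weight or GFR at diagnosis are to be taken from.

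The only other time statement is "Study period: 6-12 months after protocol acceptance".

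**The concern.** The two sources do not join. Three months lie between them, and no section assigns those months to either part or explains why they are left out. This sits badly with a stated intention to include every child in the department.

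Two things follow if the text is applied literally. First, a child who presented in January to March 2021 and did not attend from April onward is never identified. That child is missing from the pattern table and from the presentation figures, and describing presentation is the first part of the stated aim. Several diagnostic groups hold only one to four children, so one missed case would be visible there.

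Second, a child diagnosed in those months who was still attending in April enters through the prospective window, but the diagnosis visit lies in neither source. The height, weight and GFR tables all compare a value at diagnosis with one at follow-up. For such a child the plan does not say where the first value comes from, and two people abstracting the data could choose differently.

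**Working it through.** **Inputs.** Record window: 2015 to 2020 (Methods), read as January 2015 to December 2020. Prospective window: April to December 2021 (Methods). Children reported: 58 (Results). Follow-up: 6 to 132 months, median 12 (Results). The plan states no coverage figure of its own to reproduce. As a check on the denominator, the group sizes in the pattern table add up to the stated total: 27 + 16 + 1 + 6 + 3 + 4 + 1 = 58.

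**Step 1: months covered.**
- Records: 6 years × 12 = 72 months.
- Prospective: April to December 2021 = 9 months.
- Span from January 2015 to December 2021: 7 × 12 = 84 months.
- Uncovered: 84 − (72 + 9) = 3 months, which are January, February and March 2021. 3/84 = 3.6%.

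If the record window closed earlier in 2020, the gap would only widen, to at most 15 months (January 2020 to March 2021).

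**Step 2: can another passage bridge the gap?** The study period of 6 to 12 months runs forward from protocol acceptance. The document is dated 12 April 2021 and describes ethics submission as still to come, so this period does not reach back to January 2021.

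**Step 3: likely number of children.** The documents give no diagnosis dates, so accrual has to be assumed.
- Even over all 84 months: 58 × 3/84 = 2.1.
- The 58 arising only from the 81 covered months: 58/81 × 3 = 2.1.
- Assumed range of 4 to 12 diagnoses a year: 4 × 3/12 = 1 to 12 × 3/12 = 3.

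These figures count diagnoses falling in the gap. The number seen only in the gap would be smaller and cannot be derived from the documents.

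**Step 4: which results each kind of child touches.**
- Diagnosed in January to March 2021 and followed to the end of December 2021: about 9 to 12 months of follow-up. That is above the reported minimum of 6 and close to the median of 12, so the child belongs in the growth and GFR comparisons, with a first value for which the plan names no source.
- Seen only in January to March 2021: at most 3 months of observation, below the reported minimum of 6. The child affects the pattern and presentation counts, not the growth and GFR comparisons.

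**The case against.** The strongest reply is that the windows select children and do not bar earlier measurements. A child diagnosed in February 2021 and attending in April is included, and the unit's own chart would normally hold the diagnosis values. Taking age at diagnosis by history shows that the plan expects information from before the visit. The Results point the same way: a longest follow-up of 132 months exceeds the 84 months from January 2015 to December 2021. Either data from outside the windows were used, or that figure is wrong (the largest maximum in the pattern table is 36 months). It can also be said that closing record review at a year end and starting prospectively in April is an ordinary practical arrangement.

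Much of this stands. The diagnosis value is left undefined by the plan, but it is not shown to be unobtainable. What remains is that no section says any of this, and the reply does nothing for a child seen only in the gap.

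A reader might infer more in three ways.

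- **That the growth and GFR results are biased**, because first values were taken late or because children who stopped attending were lost. The documents support neither. Nothing says that an April or later visit replaced the diagnosis visit, and children seen only in the gap fall below the shortest reported follow-up.
- **That final visits falling in those months were dropped.** This needs a child already in the records who was last seen in January to March 2021 and never came back. The documents give no such case and no count.
- **That about 7 children are affected.** The group medians guarantee at least 14 + 8 + 1 + 3 + 2 + 4 + 0 = 32 children with 12 months or more, so at most 58 − 32 = 26 have less. For follow-up of 6 to 11 months ending in April to December 2021, diagnosis falls in the gap in 3 + 3 + 3 + 3 + 2 + 1 = 15 of 54 combinations, and 15/54 × 26 = 7.2. The arithmetic is right, but it takes the largest possible 26, assumes that all of them ended follow-up in the prospective window, and spreads lengths and end months evenly. If those children came from the 2015 to 2020 records, the number is 0. It also counts diagnoses in the gap, not wrong baselines.

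**Conclusion.** The gap is real but minor. On the ordinary reading of the record window, three months are covered by neither source, which does not fit the statement that all children are included. The consequences that follow from the text are a possible undercount in the pattern and presentation tables, and an unstated source of diagnosis values for children diagnosed in those months who enter prospectively.

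A fair scale is about 2 of 58 diagnoses. It rests on the assumption of even accrual, since the documents give no diagnosis dates. They do not show that any child was lost or given a wrong baseline, and they give no ground for calling the growth or GFR comparisons biased.

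**What to change.** Change the record window to January 2015 to 31 March 2021, so that it meets the prospective window. State that diagnosis height, weight and GFR for children diagnosed in January to March 2021 come from those charts. Add any eligible child found to the pattern and presentation tables. If those charts have already been reviewed, one sentence saying so closes the point.

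The cost is one changed date and three more months of chart review in the same unit. The cohort total and some counts may change slightly.
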